a. Subjects in Cohort 2 randomized to Hib vaccine will not receive a vaccination at Visit 3. These subjects may receive a third dose of Hib vaccine according to local practice or national recommendations, at the discretion of the investigator.

b. Subjects in Cohort 3 randomized to Hib vaccine will not receive a vaccination at Visit 2.

STATISTICAL ANALYSIS

All of the analyses will be summarized for each cohort separately.

Immunogenicity Analysis Populations

An evaluable immunogenicity population and an all-available immunogenicity population will be defined for the immunogenicity analyses separately. The evaluable immunogenicity population will be the primary population for the immunogenicity analyses.

Safety Analysis

The safety population will be defined for safety analysis. The safety population will include all subjects who receive at least 1 dose of an investigational product.

Analysis Timing:

The primary analysis will be performed when the following data are available:

- IgG immunogenicity data 1 month after the infant series in Cohort 1;
- IgG immunogenicity data 1 month after the last dose of 13vPnC in Cohorts 2, 3, 4;
- Safety data up to 6 months after the last study vaccination for Cohorts 2, 3 and 4.

SCHEDULE OF ACTIVITIES

The schedule of activities table provides an overview of the protocol visits and procedures. Refer to the Study Procedures and Assessments sections of the protocol for detailed information on each procedure and assessment required for compliance with the protocol. The investigator may schedule visits (unplanned visits) in addition to those listed on the schedule of activities table, in order to conduct evaluations or assessments required to protect the well-being of the subject.

Visit Number	1	2	3	4	5	6	7	8 to 11
Visit Description	Vaccination	Vaccination	Vaccination	Post-	Vaccination	Post-Toddler	6-Month	Persistence
	1	2	3	Infant	4	Dose Visit	Follow-up	Blood Draws ^a
				Dose			Telephone	
x 74 4, xx 74 x	10 1 51	10 / 50	42 / 50	Visit	265 1 155	00 / 10 D	Contact	
Visit Window	42 to 56	42 to 70	42 to 70	28 to 42	365 to 455	28 to 42 Days	168 to 196 Days	Annually After
	Days of Age	Days After Visit 1	Days Alter Visit 2	Days	Days	After visit 5	Alter Last Study	VISIT 5
		v Isit I	v 1810 2	Visit 3	of Age		vaccination	
Informed consent	Х							
Review inclusion/exclusion criteria	Х							
Demography, medical history, and	Х							
physical examination								
Record nonstudy vaccines	Х	Х	Х	Х	Х	Х	Х	

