Prevenar 13, the 13-valent pneumococcal conjugate vaccine (13vPnC) was approved in China in October 2016 for the prevention of invasive pneumococcal disease in infants 6 weeks to 15 months of age. The approved regimen only allows vaccination with Prevenar 13 at 2, 4, 6 months for the primary series and the toddler or booster dose at 12 to 15 months of age. Prevenar, the 7-valent vaccine that was used as a comparator in the Phase 3 study in China had been approved through 5 years of age (up to the 6th birthday). The safety and immunogenicity of 7vPnC in children 7 months up to 5 years of age had been assessed in a post-licensure study (Study number B1841008).

The Center for Drug Evaluation (CDE) requested that safety and immunogenicity of Prevenar 13 be assessed in children 7 months to 5 years of age (before the 6th birthday). CDE also requested that Pfizer provide antibody persistence data through 5 years of age in children vaccinated as infants. This study is designed to support licensure of 13vPnC from

7 months through 5 years of age and to address both of these post licensure commitments from the CDE.

This study includes 4 separate cohorts broken down by age. Cohorts 2, 3 and 4 range in age from 7 months to 5 years of age (Cohort 2 - 7 months to <12 months of age; Cohort 3 - ≥ 1 year to <2 years; Cohort 4 - ≥ 2 years to <6 years of age). These three cohorts are of primary interest in obtaining licensure in the 7 months to 5 year age range and addressing the CDE request to obtain safety and immunogenicity data in this age group. Immune responses before and after the last vaccination in each of these age groups will be measured and used as a surrogate of efficacy. Cohort 1 will include infants 6 weeks to 2 months of age that will be vaccinated with 13vPnC according to the currently licensed infant schedule (2, 4, 6 and 12 to 15 months). Post vaccination serotype specific serum anticapsular IgG responses in Cohorts 2, 3, and 4 will be compared to the post infant series responses in Cohort 1 as a bridge to efficacy. Cohorts 2, 3, and 4 will also include a control group vaccinated with *Haemophilus influenzae* type b (Hib) vaccine. The Hib vaccinated infants and children will serve as controls for assessment of the safety and immunogenicity of Cohorts 2, 3, and 4.

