- The investigator or an authorized designee completes the CRF and updates the investigational product accountability records.
- The e-diary data should be viewed online via the vendor portal at frequent intervals from Day 1 to Day 7 after vaccination to evaluate e-diary completion and compliance and as part of the ongoing safety review.

6.2.2. Cohort 2: Visit 2, Vaccination 2 (At Least 28 Days After Visit 1)

- Review the subject's e-diary data since the previous visit.
- Based on clinical evaluation, determine whether any AEs (including SAEs) have occurred since the last study visit and record them on the CRF.
- Record any nonstudy vaccinations.
- On the day of vaccination, measure and record the subject's axillary temperature.
- Ensure that the subject continues to be eligible for the study; refer to Subject Withdrawal section of the protocol.
- Ensure the subject does not meet any of the temporary delay criteria.
- Administer a single intramuscular dose of investigational product (13vPnC or Hib) into the subject's left limb (left anterolateral thigh muscle or deltoid of the left arm) in accordance with the local package insert.
- Observe the subject for at least 30 minutes after vaccination for any significant acute reactions. Any AE noted during the observation period should be recorded in the source documents and in the AE section of the CRF.
- Issue a measuring device and a digital thermometer (if necessary) to the caregiver and provide instructions on their use.
- Issue a subject e-diary (if necessary) to the caregiver and provide instruction on its completion.
- Ask the caregiver to contact the investigator or other site staff immediately if any significant illness or hospitalization occurs during the study period, or if the subject reports redness or swelling at the investigational product injection site measuring >14 units on the measuring device.
- Remind the caregiver to bring the e-diary to the next study visit.
- The investigator or an authorized designee completes the CRF and updates the investigational product accountability records.
- The e-diary data should be viewed online via the vendor portal at frequent intervals from Day 1 to Day 7 after vaccination to evaluate e-diary completion and compliance and as part of the ongoing safety review.

6.2.3. Cohort 2: Visit 3, (365 Days to <450 Days of Age and at Least 56 Days After Visit 2)

• Review the subject's e-diary data since the previous visit.

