In summary, as shown in above in Table 12, Table 13, and Table 14, 100 evaluable subjects vaccinated with 13vPnC are needed for each cohort. Assuming a nonevaluable rate of approximately 20% for Cohort 1 and 15% for Cohort 2, 3, and 4, with a 2:1 randomization ratio within Cohort 2, 3, and 4, a total of 125, 177, 177, and 177 subjects should be randomized in Cohorts 1, 2, 3, and 4, respectively, to ensure the required number of evaluable subjects to declare the non-inferiority of 13vPnC in the age of 7 months to <6 years relative to the infant group (Cohort 1) with regard to immunogenicity. For the OPA a random subset of 50 blood samples from subjects randomized to receive 13vPnC in cohorts 1 through 4 will be selected for OPA testing. For subjects who are randomized to receive Hib in Cohorts 2 to 4 a random subset of 25 blood samples from each cohorts will be selected for OPA testing.

Table 15. Planned Enrollment

	13vPnC	Control	Total
3+1 regimen (Cohort 1)	125	N/A	125
2+1 regimen (Cohort 2)	118	59	177
1+1 regimen (Cohort 3)	118	59	177
1-Dose regimen (Cohort 4)	118	59	177
Total	479	177	656

Enrollment (Approximately 20% Nonevaluable Rate for Cohort 1 and 15% Nonevaluable Rate for Cohort 2, 3, and 4)

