2.2. Study Design

- This is a phase 3 randomized, open-label study to evaluate the safety, tolerability, and immunogenicity of 13vPnC in infants and young children who are naïve to pneumococcal vaccination.
- Subjects will be stratified into 4 cohorts defined by their age pleat consent:
 - Cohort 1: Subjects 6 weeks (42 days) to 2 months (56 days) of age;
 - Cohort 2: Subjects 7 months (210 days) to <12 months (<365 days) of age;
 - Cohort 3: Subjects ≥ 1 year to ≤ 2 years of age;
 - Cohort 4: Subjects ≥ 2 years to <6 years of age.

- Subjects in Cohort 1 will all receive 13vPnC at 2, 4, 6 and 12 to 15 months of age. See Table 2 below.
- Subjects in Cohorts 2, 3, and 4 will be randomized into 2 groups in a 2:1 ratio to receive 13vPnC or comparator (Hib vaccine) according to age-appropriate schedules. See Table 2 below.

		Age at first vaccination	Age at second vaccination	Age at third vaccination	Age at fourth vaccination
Cohort 1	13vPnC	42 to 56 Days of	42 to 70 Days After	42 to 70 Days	365 to 455
		Age	Visit 1	After Visit 2	Days of Age
Cohort 2	13vPnC or	7 to <12 Months	At Least 28 Days	365 Days to <450 Days	
	Hib	of Age	After Visit 1	of Age and at Least 56	
		_		Days After Visit 2 ^a	
Cohort 3	13vPnC or	≥ 1 to <2 Years	At Least 56 Days		
	Hib	of Age	After Visit 1 ^b		
Cohort 4	13vPnC or	≥ 2 to <6 Years			
	Hib	of Age			

Table 2. Age at Vaccination

a. Subjects in Cohort 2 randomized to Hib vaccine will not receive a vaccination at Visit 3. These subjects may receive a third dose of Hib vaccine according to local practice or national recommendations, at the discretion of the investigator.

b. Subjects in Cohort 3 randomized to Hib vaccine will not receive a vaccination at Visit 2.

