6.4. Safety Summaries and Analyses

All safety analyses will be summarized based on the safety population in accordance with Pfizer reporting standards. All safety summaries will be provided by vaccine group separately for each dose in infant series and toddler dose.

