6.4.2. Reactogenicity Data

The derived endpoints (Section 3.4.2) for each local reaction, systemic event, and use of antipyretic/pain medication to prevent or treat symptoms will be summarized.

The presence and maximum severity of the local reaction and systemic event at "any day (Day 1 - Day 7)" for each vaccination (13vPnC or Hib) following each dose in Cohort 2, 3, 4 will be summarized by proportions of subjects with the associated 95% Clopper-Pearson CIs.

The presence of each local reaction and systemic event on any day (Day 1-7), any local reaction on any day (Day 1-7), maximum severity of each local reaction and systemic event on any day (Day 1-7) following any vaccination in Cohort 2, 3, 4 will also be summarized by proportions of subjects with associated Clopper-Pearson CIs. For local reactions, systemic events, and use of antipyretic/pain medication to prevent or treat symptoms, descriptive summary statistics of the maximum duration of the event will be provided.

For the onset of local reactions, systemic events, and use of antipyretic/pain medication to prevent or treat symptoms, descriptive summary statistics of the onset day will be provided.

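### The 'any vaccination' reactogenicity summary in SAP 6.4.2 sets more 13vPnC doses beside fewer Hib doses in Cohorts 2 and 3, so the schedule alone can show an excess on 13vPnC

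*SAP*

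**What the plan says.** SAP 6.4.2 specifies two layers of reactogenicity summary. The first gives presence and maximum severity over Days 1 to 7 "for each vaccination (13vPnC or Hib) following each dose in Cohort 2, 3, 4 will be summarized by proportions of subjects", with Clopper-Pearson intervals. The second covers each reaction, any local reaction and maximum severity "following any vaccination in Cohort 2, 3, 4 will also be summarized by proportions of subjects". The SAP 6.4 introduction adds: "All safety summaries will be provided by vaccine group". SAP 5.2.1 and 6.1.2.1 likewise give a proportion and interval for each vaccine group.

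The study schedules differ between the randomised groups:

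- **Cohort 2.** Both groups are vaccinated at Visits 1 and 2 (Protocol 6.2.1 and 6.2.2), and 13vPnC recipients have a further dose at Visit 3. Protocol Table 5, footnote a: "Subjects in Cohort 2 randomized to Hib vaccine will not receive a vaccination at Visit 3". Any third Hib dose is given outside the study (Protocol 6.2.3).
- **Cohort 3.** 13vPnC is given at Visits 1 and 2. SAP 2.2, Table 2, footnote b: "Subjects in Cohort 3 randomized to Hib vaccine will not receive a vaccination at Visit 2".
- **Cohort 4.** Each group has one dose.

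Diary recording after the extra visit is for 13vPnC recipients only (Protocol Tables 2 and 3, footnotes). SAP 6.4.2 contains no matched-dose version of the any-vaccination summary, no adjustment for number of doses and no caveat.

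On the purpose of the Hib groups, Protocol 1.2 says: "The Hib vaccinated infants and children will serve as controls for assessment of the safety and immunogenicity of Cohorts 2, 3, and 4".

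**The concern.** A proportion of children with at least one reaction grows with the number of doses observed. Two columns side by side, one accumulated over an extra dose and an extra seven diary days, look like a comparison of vaccines but also compare schedule lengths. The same holds for maximum severity, since one more dose is one more chance of a higher grade.

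At stake is how the reactogenicity of 13vPnC reads in Cohorts 2 and 3. This is the only planned reactogenicity summary that pools over doses, and an apparent excess in it could be put down to the vaccine when the regimen explains it. Nor does the SAP plan a difference between groups with an interval for reactogenicity, which would give a reader a proper contrast to set against it. Risk differences are specified for tier 1 and tier 2 adverse events only (SAP 5.2.1 and 6.4.1).

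**Working it through.** **Inputs from the documents.** Study doses, 13vPnC against Hib: 3 v 2 (Cohort 2), 2 v 1 (Cohort 3), 1 v 1 (Cohort 4). At 7 diary days per dose, this is 21 v 14, 14 v 7 and 7 v 7 days.

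Group sizes: Protocol 9.5 needs 150 evaluable subjects per cohort with 15% nonevaluable. 150 / 0.85 = 176.5, rounded up to 177, which reproduces the plan's figure. Split 2:1, it gives 118 and 59, as in Protocol Table 15.

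**Assumptions.** The documents give no per-dose reaction rate *p* and no within-child correlation *ρ* between doses. I take *p* and *ρ* as equal in the two groups, so any difference comes from the schedule alone.

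**Independent doses (ρ = 0).** P(any reaction in *k* doses) = 1 − (1 − p)^k. The excess is p(1 − p)² in Cohort 2 and p(1 − p) in Cohort 3.

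| p per dose | Cohort 2: 3 v 2 doses | Excess (points) | Cohort 3: 2 v 1 doses | Excess (points) |
|---|---|---|---|---|
| 10% | 27.1% v 19.0% | 8.1 | 19.0% v 10.0% | 9.0 |
| 20% | 48.8% v 36.0% | 12.8 | 36.0% v 20.0% | 16.0 |
| 30% | 65.7% v 51.0% | 14.7 | 51.0% v 30.0% | 21.0 |
| 50% | 87.5% v 75.0% | 12.5 | 75.0% v 50.0% | 25.0 |

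The maximum is 14.8 points in Cohort 2 (at p = 1/3) and 25 points in Cohort 3 (at p = 1/2).

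**Correlated doses.** Under a beta-binomial model with a = p(1 − ρ)/ρ and b = (1 − p)(1 − ρ)/ρ, the chance of no reaction in *k* doses is the product of (b + i)/(a + b + i) for i = 0 to k − 1. At p = 20% and ρ = 0.5, a = 0.2 and b = 0.8. The chance of no reaction is then 0.80, 0.72 and 0.672 for one, two and three doses, so the chance of any reaction is 20.0%, 28.0% and 32.8%. The excess is 4.8 points in Cohort 2 and 8.0 in Cohort 3. Over the range of ρ at p = 20%:

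| ρ | Cohort 2 excess (points) | Cohort 3 excess (points) |
|---|---|---|
| 0 | 12.8 | 16.0 |
| 0.3 | 7.4 | 11.2 |
| 0.5 | 4.8 | 8.0 |
| 0.8 | 1.7 | 3.2 |
| 1 | 0 | 0 |

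**Size against sampling error.** These are Wald 95% intervals that a reader might form from the two columns if the expected proportions were observed, at p = 20%:

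- Cohort 3, ρ = 0, 118 v 59: SE = √(0.36×0.64/118 + 0.20×0.80/59) = 0.068, so 16.0 points with interval 2.6 to 29.4.
- Cohort 3, ρ = 0.5, 118 v 59: SE = √(0.28×0.72/118 + 0.20×0.80/59) = 0.066, so 8.0 points with interval about −5 to 21.
- Cohort 2, ρ = 0, 118 v 59: SE = √(0.488×0.512/118 + 0.36×0.64/59) = 0.078, so 12.8 points with interval about −2 to 28.

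SAP Section 2 repeats all summaries with 177 more subjects in Cohort 2 and 73 more in Cohort 3. If these were also split 2:1, the groups become 236 v 118 and 167 v 83. At ρ = 0 the intervals are then about 2 to 24 points in Cohort 2 and 5 to 27 in Cohort 3. At that extreme, a difference due only to the schedule would look real in both cohorts.

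**Matched doses.** Restricted to doses 1–2 in Cohort 2 and dose 1 in Cohort 3, *k* is the same in both groups. The expected difference is then zero for every *p* and *ρ*.

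**The case against.** The strongest reply is that the fair data are already planned. The primary safety endpoint concerns the 7 days after each vaccination, and the per-dose tables in SAP 6.4.2 show both groups at every dose they share, with the 13vPnC-only dose on its own. The any-vaccination summary is an addition. SAP 5.1 calls the study descriptive with no decision rules, and no between-group test is attached to this table. Each column is also a correct estimate of the chance of a reaction over that group's own study schedule.

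All of this stands, and it limits the point to presentation. It does not remove it, because the table has no label or matched-dose row to stop a reader comparing unlike columns.

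Stronger readings are tempting, but the documents do not support them:

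- A reader might infer that the Hib control goes unused. It is compared with 13vPnC for tier 1 and tier 2 adverse events and for immunogenicity (SAP 5.2.1 and 5.2.2), and it is tabulated per dose for reactogenicity.
- A reader might infer that the valid reactogenicity contrast cannot be obtained. The point difference at each shared dose can be read from the per-dose tables. What is missing is its interval, and a pooled figure over the two shared doses in Cohort 2.
- A reader might assume that the pooled row will be the headline result. Nothing in the documents says so.
- A reader might take the independent-dose figures as the expected size. They are one end of a range, and at correlation 0.5 the Cohort 3 interval at the original sizes includes zero.

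**Conclusion.** The point holds as a modest, inexpensive improvement. In Cohorts 2 and 3 the any-vaccination columns are not like for like, and equal per-dose rates would show as an excess on 13vPnC unless reactions to successive doses were perfectly correlated within a child. At an assumed 20% per dose, the excess runs from about 13 points (Cohort 2) and 16 points (Cohort 3) with independent doses down to about 2 and 3 at correlation 0.8. The direction follows from the dose counts. The size rests on a rate and a correlation that the documents do not give.

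No hypothesis test, primary endpoint definition or decision rule is affected, and Cohort 4 is untouched. The weakness is a misleading display, together with the lack of any planned between-group interval for reactogenicity in a trial that enrols randomised safety controls.

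**What to change.** In SAP 6.4.2, define the between-group summary over the doses both groups receive: doses 1–2 in Cohort 2, dose 1 in Cohort 3 and the single dose in Cohort 4. Give the risk difference with the Miettinen and Nurminen 95% interval that SAP 5.2.1 already specifies for tier 2 adverse events, and treat maximum severity over the same doses. Report the 13vPnC full-schedule any-vaccination rate separately. Failing that, state the number of study doses and diary days per group in the table.

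SAP Section 2 says that the primary-report analyses had already been performed. The supplemental report, which repeats them, is therefore the natural place for the matched-dose table, identified there as an addition.

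The cost is a small amount of extra table programming and a few more descriptive intervals without multiplicity adjustment, consistent with SAP 5.1. No data collection, visit or vaccination changes.

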6.4.3. Unscheduled Visits (Unplanned Visits) for Severe Reactions

A listing will be generated for all of the subjects with unscheduled/unplanned visits because of severe (Grade 3) and Grade 4 reactions.

6.4.4. Immediate AEs

Descriptive summaries and listing of subjects reporting AEs during the protocol-specified first 30-minute observation period will be summarized by vaccine group after each dose for each cohort. Also, Clopper-Pearson 95% CIs will be included with the percentages.

6.4.5. Newly Diagnosed Chronic Medical Conditions

Descriptive summary tables and listings will be provided for subjects reporting newly diagnosed chronic medical conditions that occur from 1 month to 6 months after vaccination 4 in Cohort 1.

6.4.6. Physical Examinations, Including Vital Signs

Descriptive summary tables will be provided in accordance with Pfizer reporting standards.

6.4.7. Nonstudy Vaccination and Nonstudy Medication

Nonstudy vaccination and nonstudy medication summaries will be provided with descriptive summaries. Each vaccine will be summarized according to the Anatomic Therapeutic Chemical (ATC) 4 classification system. The number and percentage of subjects receiving each vaccine will be tabulated for each vaccine group and total sample for each cohort. The denominator for the percentages is the number of subjects in the vaccine group or total sample in each cohort.

6.4.8. Hospitalization

Hospitalization during the study will be listed for each vaccine group separately for each cohort.

6.4.9. Death

Deaths during the study will be listed for each vaccine group separately for each cohort.

7. INTERIM ANALYSES

7.1. Introduction

This is a Phase 3, randomized, open-label study. In addition to the planned analyses described in Section 7.2, some analyses may be performed to support regulatory interactions.

7.2. Interim Analyses and Summaries

No formal interim analysis will be conducted for this study. However, as this is an openlabel study, the sponsor may conduct unblinded reviews of the data during the course of the study for the purpose of safety assessment or to support clinical development. This includes compilation of results of the infant series before completion of the toddler dose.

The primary analysis will be performed when the following data are available:

- IgG immunogenicity data 1 month after the infant series in Cohort 1;
- IgG immunogenicity data 1 month after the last dose of 13vPnC in Cohorts 2, 3, 4;
- Safety data up to 6 months after the last study vaccination for Cohorts 2, 3 and 4.

The above data will be summarized in the primary study report and will be submitted to regulatory authorities to support licensure of 13vPnC in infants and children 15 months to 5 years of age. Type I error of the study will all be spent for this primary analysis. In addition, supplemental summaries of immunogenicity and safety data may be generated to support renewal of the 13vPnC license.

Additionally, other data from the study that were not included in the primary report for 13vPnC licensure for infants and children 15 months to 5 years and summary reports for the 13vPnC renewal package will be analyzed and reported separately once all subjects have completed the study and all data are available. No changes to the study design or conduct of the study are intended to be made based on these results. The study will continue for the remaining subjects regardless of the results submitted to the regulatory authorities.

All analyses included in the final study report will be purely descriptive; therefore, no type I error adjustment is needed.

A list of protocol deviations will be compiled prior to the primary analysis, and will be updated prior to the final analysis. Subjects who do not meet the eligibility criteria and subjects who have major protocol violations will be excluded from the evaluable immunogenicity population. A major protocol violation is a protocol violation that, in the opinion of the clinicians, would materially affect assessment of immunogenicity, eg, subject receipt of a prohibited vaccine or medication that might affect immune response or a medication error with suspected decrease in potency of the vaccine. Clinicians will identify those subjects with protocol violations before the primary analyses and the final analysis of immunogenicity results.

